## STATEMENT OF COMPLIANCE

The trial will be conducted in accordance with International Conference on Harmonization Good Clinical Practice (ICH GCP) and applicable United States (US) Code of Federal Regulations (CFR). The Principal Investigator will assure that no deviation from, or changes to, the protocol will take place without prior documented approval from the Institutional Review Board (IRB), except where necessary to eliminate an immediate hazard(s) to the trial subjects. All personnel involved in the conduct of this study have completed Human Subjects Protection and ICH GCP Training.

The protocol, informed consent form(s), recruitment materials, and all subject materials will be submitted to the local Institutional Review Board (IRB) for review and approval. Approval of both the protocol and the consent form must be obtained before any subject is enrolled. Any amendment to the protocol will require review and approval by the IRB before the changes are implemented to the study. All changes to the consent form will be IRB approved; a determination will be made regarding whether a new consent needs to be obtained from subjects who provided consent, using a previously approved consent form.

## 1 PROTOCOL SUMMARY

### 1.1 SYNOPSIS

Title:	Nerve block with liposomal bupivacaine yields fewer complications and similar pain relief when compared to an interscalene catheter for arthroscopic shoulder surgery: a randomized controlled trial
Study Description:	This is a blinded, randomized controlled trial to compare the control arm (continuous ropivacaine ISC) to the experimental arm (single-injection, brachial plexus nerve block using liposomal bupivacaine) in patients undergoing outpatient arthroscopic shoulder surgery at a single, tertiary academic institution.
Objectives:	

• Compare complication rates

• Compare pain level, dose frequency of prescribed opioid analgesics, consumption of prescribed nonopioid analgesics, quantity and quality of sleep, and overall satisfaction with pain control

• Compare patient-reported outcome measures

Endpoints:	

• Patient reported complications on post-op day 0, 1, 2, 3, and 4

• Visual Analog Scale, prescribed opioid analgesic dose frequency, consumption of prescribed nonopioid analgesics, hours of uninterrupted sleep, subjective quality of sleep (0-10 scale), and pain control overall satisfaction (five-point Likert scale) on post-op day 0, 1, 2, 3, and 4

• Visual Analog Scale, Single Assessment Numeric Evaluation, American Shoulder and Elbow Surgeons Standardized Shoulder Assessment Form, and Penn Shoulder Score at 12 weeks post-op

Study Population:	Patients greater than 19 years of age undergoing outpatient arthroscopic shoulder surgery
Phase:	Not Applicable

Description of Study Intervention:	Patients in the ISC arm will have a 19 gauge Arrow Continuous Nerve Catheter (Teleflex, Wayne, PA, USA) placed with a bolus of 15-20 mL of 0.5% ropivacaine given through the needle prior to threading the catheter. An elastomeric, basal-only, On-Q infusion pump (Avanos Medical, Alpharetta, GA, USA) with 0.2% ropivacaine will be started in the post-anesthesia care unit at 8 mL/hour, and the catheter will be removed by the patient after two days. For patients in the LB arm, 10 mL (133 mg) of liposomal bupivacaine (Pacira BioSciences, Parsippany, NJ, USA) mixed with 7 mL (35 mg) bolus of 0.5% bupivacaine will be injected.
Study Duration:	January 1, 2020 to December 1, 2021
Subject Duration:	3 months

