## 1.2 SCHEDULE OF ACTIVITIES (SOA)

- *Screening/Consent Visit*
- *Randomization Visit*
- *Day of Surgery Visit*
- *Call 1: Evening after surgery (Day 0)*
- *Call 2: Day 1 morning*
- *Call 3: Day 1 evening*
- *Call 4: Day 2 morning*
- *Call 5: Day 2 evening*
- *Call 6: Day 3 morning*
- *Call 7: Day 3 evening*
- *Call 8: Day 4 morning*
- *Call 9: Day 4 evening*

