## 3 STUDY DESIGN

### 3.1 OVERALL DESIGN

Patients undergoing arthroscopic shoulder surgery were prospectively assessed after randomization into either ropivacaine ISC or single-injection liposomal bupivacaine brachial plexus nerve block (LB) arms. All patients were

discharged with 5 analgesics (acetaminophen, methocarbamol, gabapentin, acetylsalicylic acid, and oxycodone) for as-needed pain relief. Preoperatively, patient demographics and baseline Visual Analog Scale, Single Assessment Numeric Evaluation, American Shoulder and Elbow Surgeons, and Penn Shoulder Scores were obtained. For the first four days postoperatively, complication rates (nausea, dyspnea, anesthetic site discomfort and/or irritation and/or leakage, and self-reported concerns and complications), pain, medication usage, and sleep data were assessed by phone survey every 12 hours. The primary outcome was overall complication rate. At 12 weeks postoperatively, Visual Analog Scale, Single Assessment Numeric Evaluation, American Shoulder and Elbow Surgeons, and Penn scores were reassessed. Outcome scores were compared with Mann-Whitney U tests, and demographics were compared with chi-squared tests. Significance was set at  $P < .05$ .

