## 7 STUDY ASSESSMENTS AND PROCEDURES

## 7.1 STUDY ASSESSMENTS

- twice-daily phone calls for the first 4 days post-surgery

At each phone call, the following surveys will be performed:

- Medication Intake Survey
  - Since the last phone call:
    - Which medications have been consumed?
    - How many pills?
- Pain Survey
  - On a scale of 1-10, with 10 being the worst, what is your pain right now?
- Sleep Quality Survey
  - On a scale of 0-5, with 5 being the best, how was your sleep last night?
  - How many hours were you able to sleep before being interrupted by pain?

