## 8 STATISTICAL CONSIDERATIONS

### 8.1 STATISTICAL HYPOTHESES

- Primary Efficacy Endpoint(s): Postoperative Pain Scores
- Secondary Efficacy Endpoint(s): Postoperative Oral Morphine Equivalents, Analgesia Satisfaction, Analgesia Complications, Sleep Quality, and Hours of Painless Sleep

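### The title claims similar pain relief, but pain is analysed only by difference tests, with no margin, effect estimate or confidence interval planned

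*Combined protocol and SAP*

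**What the plan says.** The title in section 1.1 states a two-part result: the LB block "yields fewer complications and similar pain relief when compared to an interscalene catheter". The matching objective in the same section is only comparative: "Compare pain level, dose frequency of prescribed opioid analgesics, consumption of prescribed nonopioid analgesics, quantity and quality of sleep". It sets no direction and no similarity hypothesis.

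The analysis in section 3.1 is "Outcome scores were compared with Mann-Whitney U tests". Section 8.3 repeats this for perioperative pain, medication use, sleep, satisfaction and the 12-week scores, with significance at P < .05. Section 8.1 is headed as hypotheses but lists endpoints only, among them "Primary Efficacy Endpoint(s): Postoperative Pain Scores". Section 8.2 gives power 0.8 and alpha 0.05, based on complication rates from earlier literature. Section 2.3.2 mentions superiority or non-inferiority as a possible finding, without a margin or a test.

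Pain is asked at each call (section 7.1): "On a scale of 1-10, with 10 being the worst, what is your pain right now". The synopsis calls the measure a Visual Analog Scale. Section 1.2 lists nine calls, from the evening of surgery to the evening of day 4.

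**The concern.** A Mann-Whitney test can give evidence that two arms differ. When it does not reject, the P value alone cannot separate a small true difference from too little information. A claim of similarity needs an interval for the difference and a limit to judge it against, and the plan has neither.

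The other outcomes do not fill the gap. Pain scores are recorded while patients take five drugs "for as-needed pain relief", so analgesic use matters to any statement about relief. But medication use, sleep and satisfaction get the same kind of test.

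At stake is the balance that the title offers: fewer complications at no cost in pain control. If the pain half rests on a non-significant P value, readers cannot see how much worse pain under LB could still be.

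**Working it through.** **The texts side by side.** The plan gives no figure for pain that could be reproduced.

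| Needed for a similarity claim | In the documents |
|---|---|
| Hypothesis | None; 8.1 lists endpoints |
| Margin | None; 2.3.2 names non-inferiority without one |
| Estimate and interval | None in 3.1 or 8.3 |
| Sample size set for pain | None; 8.2 uses complication rates |

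The non-inferiority statement in section 2.2 concerns earlier shoulder-replacement studies. ANCOVA and least-squares means appear only in the abbreviation list (9.2).

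**Illustration; every input is assumed.** One pain score per patient, so no within-patient correlation enters; normal scores; equal arms; two-sided 5%. The 95% CI half-width for the difference is 1.96 × SD × √(2/n). At P = .05 the estimate lies one half-width from zero, so the far limit lies two half-widths away.

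| n per arm | Half-width, SD 2 / 2.5 / 3 | Far limit when P is about .05 |
|---|---|---|
| 30 | 1.01 / 1.27 / 1.52 | 2.0 / 2.5 / 3.0 |
| 50 | 0.78 / 0.98 / 1.18 | 1.6 / 2.0 / 2.4 |
| 100 | 0.55 / 0.69 / 0.83 | 1.1 / 1.4 / 1.7 |

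For example, at n = 50 and SD 2.5: 1.96 × 2.5 × √(2/50) = 0.98, and 2 × 0.98 = 1.96. With normal scores a rank-based interval is wider by √(π/3), about 2%.

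**Chance of a non-significant test when the true difference is 1 point** (SD 2.5, n multiplied by 3/π for the rank test): 67% at 30 per arm, 50% at 50 and 21% at 100. A simulation with scores rounded and clipped to 0-10, means 4.5 and 5.5, gave 69%, 53% and 21%.

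**Dependence on assumptions.** Averaging four calls narrows the interval, by an amount that the documents do not fix. At 50 per arm, scores rounded and clipped to 1-10, nominal SD 2 to 3 and correlation 0.3 to 0.7 between calls, the simulated Hodges-Lehmann half-width was 0.54 to 0.91 at a mean score of 4, but 0.44 to 0.66 at a mean of 2.5.

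**Two different claims.** Assume a margin of 1 point, true difference 0, one measurement, SD 2 to 3, 2.5% for each bound and 80% power. Non-inferiority needs 2 × SD² × (1.960 + 0.842)² = 63 to 142 per arm. Two-sided equivalence needs 2 × SD² × (1.960 + 1.282)² = 85 to 190 per arm.

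**Why one overall average is not enough.** If LB were 1.0 point worse at calls 1-5 and 1.25 better at calls 6-9, the nine-call mean difference would be (5 × 1.0 − 4 × 1.25)/9 = 0.

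**The case against.** The strongest reply is that this is one word in a title. The objective is only to compare, section 3.1 makes complications the primary outcome, and section 8.3 lists tests without ruling out other summaries. All of that is true. It limits the weight of the point, but it does not supply an analysis that could carry the claim.

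A reader might infer that the plan treats P ≥ .05 as proof of similarity. The documents contain no such rule; they simply plan nothing else that could support the word.

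A reader might also infer that a difference test says nothing about similarity at any sample size. That goes too far. With SD 2.5 and 1,000 per arm, a true difference of 0.5 point would be missed only 0.8% of the time, so non-significance there would be informative. It is informative because the interval would be narrow, and that interval is what should be reported.

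Finally, section 2.3.2 suggests a one-sided aim, so reading the title as two-sided equivalence is a choice. Either reading needs a margin, and none is given.

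**Conclusion.** The point holds on the text alone: following the plan as written cannot support the title's statement on pain. It should be fixed, because the statement is half of the trial's headline and the correction is cheap.

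The figures above only illustrate; they depend on assumed SDs, arm sizes, mean scores, correlations and a margin, none of which the documents give. They do not show that the trial is too small for pain, since no sample size is stated.

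Nor do the documents settle whether a primary or a secondary conclusion is affected. Section 3.1 names complications as primary and section 8.1 names pain. That conflict must be reconciled separately, and this point stands either way.

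**What to change.** **Section 8.3.** Keep the Mann-Whitney test. Add the LB minus interscalene catheter difference in pain as the Hodges-Lehmann estimate with a 95% CI, at the calls already scheduled for days 0 to 4, with the number of patients contributing to each.

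Show the periods before and after planned catheter removal separately, as description only. The synopsis says that "the catheter will be removed by the patient after two days" but gives no hour, so calls 1-4 fall before, calls 6-9 after, and "Call 5: Day 2 evening" stands alone. The background in section 2.2 speaks of 48-72 hours; the two statements need to be reconciled before the periods are labelled.

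**Title.** Remove the similarity claim. If P ≥ .05, write *no difference detected* and state the largest LB disadvantage that the interval still allows.

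**Section 8.1.** Use *non-inferior* or *similar* only if a margin fixed before the data were seen can be documented, with its value and date, and applied to one pre-named pain summary or with every period required to pass. Allowing a non-inferiority claim on either of two periods without adjustment would raise the chance of at least one false claim from 2.5% to about 3.5-4.3%, with the true difference at the margin in both periods, four-call averages and correlation 0.3 to 0.7 between calls. Section 8.3 already reports a normality test on the data, so label any margin chosen now as post hoc and say that the sample size in 8.2 was not set for it.

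**Cost.** Changes of wording and a few estimates from pain scores that the plan already collects; no new patients or visits. The pain conclusion may become weaker.

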## 1.2 SCHEDULE OF ACTIVITIES (SOA)

- *Screening/Consent Visit*
- *Randomization Visit*
- *Day of Surgery Visit*
- *Call 1: Evening after surgery (Day 0)*
- *Call 2: Day 1 morning*
- *Call 3: Day 1 evening*
- *Call 4: Day 2 morning*
- *Call 5: Day 2 evening*
- *Call 6: Day 3 morning*
- *Call 7: Day 3 evening*
- *Call 8: Day 4 morning*
- *Call 9: Day 4 evening*

## 2 INTRODUCTION

### 2.1 STUDY RATIONALE

Following orthopedic surgery, patients frequently experience pain and discomfort. Multiple methods of regional anesthesia are available; however, the optimal technique to adequately manage pain while minimizing complications remains under investigation in arthroscopic shoulder surgery.

### 2.2 BACKGROUND

After orthopaedic surgery, patients experience exquisite levels of pain due to the large, invasive and disruptive procedures performed on the musculoskeletal system. Perioperative and post-operative pain management has traditionally involved regional anesthesia, utilizing sodium-channel blockers such as bupivacaine or ropivacaine. However, their short-acting nature requires continuous infusion via an implanted catheter that remains in place for 48-72 hours. This catheter is undesirable because it can become dislodged, requires the patient to manage it, as well as return days after surgery for removal.

A modified form of bupivacaine that is bound to lipid (liposomal bupivacaine) has been shown to have a much longer duration of action than the traditional sodium channel blockers. It is long enough that it could cover the same duration of pain as an implanted catheter and has generated interest in its potential use to control postoperative pain. Among patients undergoing total shoulder replacement, liposomal bupivacaine has shown to be non-inferior to standard catheter treatment, but there is a paucity of information on its use in rotator cuff repair. This study is meant to investigate the use of liposomal bupivacaine after arthroscopic shoulder surgery as compared to standard, catheter-infused ropivacaine.

### 2.3 RISK/BENEFIT ASSESSMENT

#### 2.3.1 KNOWN POTENTIAL RISKS

Risks are no different than that of routine multi-modal pain control. This includes inadequate pain control, nausea, vomiting, opioid addiction, infection, headache, respiratory depression, opioid addiction, hypotension, sedation, ileus, constipation, dry mouth, and gastric ulcers.

#### 2.3.2 KNOWN POTENTIAL BENEFITS

The benefits of liposomal bupivacaine include potentially increased pain control, decreased narcotic use, and decreased catheter-associated complications including knotting and falling out. If it shows either superiority or even non-inferiority to the routine multi-modal pain management, its addition will potentially decrease adverse outcomes of current procedures.

## 3 STUDY DESIGN

### 3.1 OVERALL DESIGN

Patients undergoing arthroscopic shoulder surgery were prospectively assessed after randomization into either ropivacaine ISC or single-injection liposomal bupivacaine brachial plexus nerve block (LB) arms. All patients were

discharged with 5 analgesics (acetaminophen, methocarbamol, gabapentin, acetylsalicylic acid, and oxycodone) for as-needed pain relief. Preoperatively, patient demographics and baseline Visual Analog Scale, Single Assessment Numeric Evaluation, American Shoulder and Elbow Surgeons, and Penn Shoulder Scores were obtained. For the first four days postoperatively, complication rates (nausea, dyspnea, anesthetic site discomfort and/or irritation and/or leakage, and self-reported concerns and complications), pain, medication usage, and sleep data were assessed by phone survey every 12 hours. The primary outcome was overall complication rate. At 12 weeks postoperatively, Visual Analog Scale, Single Assessment Numeric Evaluation, American Shoulder and Elbow Surgeons, and Penn scores were reassessed. Outcome scores were compared with Mann-Whitney U tests, and demographics were compared with chi-squared tests. Significance was set at  $P < .05$ .

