### 8.2 SAMPLE SIZE DETERMINATION

A power analysis was conducted at 0.8 with an alpha of 0.05, using liposomal bupivacaine and ISC complication rates calculated from prior literature.

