### 8.3 STATISTICAL ANALYSES

Data analysis was performed using IBM SPSS Statistics for Macintosh, version 27 (IBM Corp., Armonk, NY, USA). Prior to study arm comparison, a Shapiro-Wilk test was performed, which indicated non-normally distributed data.

Patient age, BMI, operative time, perioperative pain scores, medication consumption, duration and quality of sleep, satisfaction, and preoperative and postoperative PROMs (VAS, SANE, ASES, and PSS) were compared using Mann-Whitney U tests.

Additional patient demographics, including gender, smokable tobacco consumption, intraoperative complications, ASA classification, CCI scores, surgical procedures, and 6 perioperative complications (nausea, dyspnea, anesthetic site discomfort and/or irritation and/or leakage, and self-reported complications), were compared with chi-squared tests. Graded measures, such as anesthetic site discomfort and irritation, were dichotomized based on severity, into “none-to-mild” and “moderate-to-severe” categories for analysis. Statistical significance was set to  $P < .05$ .

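### The overall complication rate, named as primary in 3.1, has no patient-level definition and no test in 8.3, which compares six complication items separately at an unadjusted P < .05

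*Combined protocol and SAP*

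**What the plan says.** - Section 3.1 (Overall Design): "The primary outcome was overall complication rate". It lists the components as nausea, dyspnea, site discomfort, irritation or leakage, and "self-reported concerns and complications". They are collected by phone every 12 hours, and section 1.2 schedules nine calls.
- Section 1.1 (Synopsis, Endpoints): "Patient reported complications on post-op day 0, 1, 2, 3, and 4".
- Section 8.1 (Statistical Hypotheses): "Primary Efficacy Endpoint(s): Postoperative Pain Scores". Complications appear there among the secondary endpoints: "Secondary Efficacy Endpoint(s): Postoperative Oral Morphine Equivalents, Analgesia Satisfaction, Analgesia Complications, Sleep Quality, and Hours of Painless Sleep".
- Section 8.2 (Sample Size Determination) bases the power calculation on complication rates, described as "using liposomal bupivacaine and ISC complication rates calculated from prior literature". It gives no rates and no sample size; the only figures are a power of 0.8 and a two-decimal alpha of 0.05.
- Section 8.3 (Statistical Analyses): "6 perioperative complications (nausea, dyspnea, anesthetic site discomfort and/or irritation and/or leakage, and self-reported complications), were compared with chi-squared tests". Graded items are split into none-to-mild and moderate-to-severe. The threshold is P < .05, with no multiplicity adjustment.
- Section 7.1 (Study Assessments): the survey for each call covers medication, pain and sleep. It has no complication question.

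**The concern.** A primary outcome needs a rule that gives each patient a value, and a test that uses it. The overall complication rate has neither. The documents do not say whether one affected call is enough, how nine calls become one event, or whether a self-reported concern counts (3.1 includes concerns, 8.3 does not). The analyst could settle these points after seeing the data, including whether to count patients or events.

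The protocol title already claims fewer complications with liposomal bupivacaine. With no single test assigned to that claim, nothing in the plan stops one significant item out of six from being offered as its support. The 5% level in 8.2 and 8.3 would then not describe the claim's error rate.

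**Working it through.** **Step 1. Match the stated primary to the stated analysis.**

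- Variable named in 3.1: one overall rate.
- Variables analysed in 8.3: nausea, dyspnea, site discomfort, site irritation, site leakage and self-reported complications. That is six variables and six chi-squared tests.
- Overall variable in 8.3: none. Section 3.1 also mentions tests, but only for outcome scores and demographics.
- Rule for combining nine calls, or six items, into one patient-level event: none in any section. The only rule is the severity split within graded items.

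This mismatch needs no arithmetic. Applying 8.3 exactly produces six item results and no result for the 3.1 primary.

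**Step 2. The plan's own figure.** The only figure to reproduce is alpha = 0.05, which holds trivially for one test. The sample size cannot be checked, because 8.2 gives neither N nor rates. Sidedness is not stated; I assume two-sided tests, so 0.025 in each direction.

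**Step 3. Error rate if any one item counts, with independent items and no true difference.**

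- Either direction: 1 − (1 − 0.05)^6 = 1 − 0.95^6 = 0.265, which is 0.265/0.05 = 5.3 times the stated level.
- Favouring liposomal bupivacaine only: 1 − (1 − 0.025)^6 = 1 − 0.975^6 = 0.141. That is 0.141/0.025 = 5.6 times the one-direction level, but 0.141/0.05 = 2.8 times the stated 5%.

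**Step 4. Allow for correlation.** The items come from the same patients and three concern the same site, so positive correlation is likely. Simulated, equally correlated test statistics give:

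| Correlation between test statistics | Any item, either direction | Any item favouring liposomal bupivacaine |
|---|---|---|
| 0 | 26.5% | 14.1% |
| 0.3 | 24.1% | 12.1% |
| 0.5 | 20.7% | 10.4% |
| 0.7 | 16.4% | 8.2% |

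**Step 5. Allow for rare items.** Simulated uncorrected chi-squared tests, all under assumed N and rates:

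- 30 to 100 per arm, item rates 5% to 30%, latent correlation 0 to 0.6: 14–28% in either direction and 7–15% in one direction. Values slightly above 26.5% arise because the uncorrected statistic can exceed its nominal level in small samples.
- 30 per arm, 5% item rates: about 14–16% and 7–8%.
- 60 per arm, 2% item rates: about 11% and 6%.

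With marked correlation (latent 0.5 or more) or item rates of 5% or less, the range is roughly 11–25% and 6–13%. One setting gave 26% (30 per arm, 10% rates, latent correlation 0.6).

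**Step 6. The alternative.** One patient-level test has a nominal error of 5%, or 2.5% in one direction. In simulation (assumed 60 per arm, item rates 10–30%, latent correlation 0–0.5), the test of at least one item per patient rejected in 5.0–5.5% of null trials.

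**The case against.** The strongest reply is that more is defined than it first appears. Sections 3.1 and 8.3 give nearly the same item list, 8.3 sets a severity cut, and a reader could take the overall rate to mean at least one item in a patient. That reading is sensible, but the plan does not state it, and 8.3 still assigns it no test.

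Other objections succeed and limit the point:

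- **Error inflation is conditional.** A reader might infer that a chance finding of fewer complications is about five times likelier than stated. The documents do not support that. They nowhere say that one significant item counts as success, although they do not exclude it. The fivefold figure also mixes levels: against the stated 5%, a result favouring liposomal bupivacaine is at most about 2.8 times as likely with independent items.
- **By-day testing is not planned.** A reader might infer that six items on five days means thirty tests. The Synopsis lists the days on which complications are reported; 8.3 specifies no by-day complication tests.
- **Power basis.** A reader might infer that 8.2 powers the trial on the overall rate. It refers only to complication rates, unquantified.
- **Counting events over calls** would break the independence that chi-squared needs, but the documents do not propose it. The point is only that they do not rule it out.
- **Concerns.** Whether they should count is for the investigators to decide. What is wrong is that 3.1 and 8.3 differ.

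**Conclusion.** The concern holds in this form: the plan names an overall complication rate as primary in 3.1, but gives no patient-level definition and no test for it. This rests on the text alone and must be fixed.

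The consequence for error rates is conditional on any one item being read as a complication difference. It is then about 26% against 5% in either direction, or about 14% against 2.5% favouring liposomal bupivacaine, for independent items tested two-sided. The figures are lower with correlated or rare items, and their size rests on sample sizes and rates that the documents do not supply.

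Two further gaps belong to the same problem. Section 8.1 names a different primary, and 7.1 does not list the questions from which the complication outcome would be built.

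**What to change.** 1. **Define the variable in 3.1 and 8.3.** One binary value per patient: at least one listed complication at any call from Call 1 to Call 9, applying the 8.3 severity cut to graded items. State which items are graded, whether self-reported concerns count (the same in both sections), and how patients with missed calls are handled.
2. **Test it once.** Use one chi-squared test, with a risk difference and 95% CI.
3. **Demote the components.** Report the six items and the by-day rates descriptively, and state that none of them alone supports a claim of fewer complications.
4. **Name one primary.** Reconcile 8.1 with 3.1.
5. **Collect the data.** Add the complication items to the call survey in 7.1, or point to the form that already holds them.
6. **Label the timing.** Section 8.3 already reports a Shapiro-Wilk result, and some references were accessed in March 2022, after the December 2021 end date in the Synopsis. If data have been analysed, the composite definition is post hoc and should be described so.

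The cost is wording in five sections at most (3.1, 7.1, 8.1, 8.3 and, for consistency, 1.1) and one derived variable, provided that complications were collected at each call as 3.1 says. If they were not, the definition cannot be applied in full. The downside for the investigators is that a single significant item no longer supports the headline claim.
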